We need to understand which version of breast screening offers the most benefit with the least harm. The best evidence for this would be from a Randomised Controlled Trial (RCT). However, such trials are very expensive, often do not include sufficient women, and need at least 10 years follow-up. So a trial that started recruiting now would not give answers until the year 2036. Instead, we suggest making use of the data available from offering different versions of breast screening to over 13 million women in England over the last 25 years, as a retrospective observational research study. We have carefully designed the design and analysis using methods that allow causal inference to be made from observational data.

The Research Plan

In this very large observational study we will analyse the records of women screened in England between 1990 and 2018, with follow up available as to whether they got breast cancer (from the English Cancer Registry) and whether they died (from the civil registration mortality file). We will analyse the ages and frequencies women are invited and the proportion of women we recall for further tests affects the benefits and harms of screening. These benefits and harms will include numbers of false positive recalls, overdiagnosed cases, and mortality. We will also analyse the mechanism of action for any changes, how changes to number and nature (eg histological grade and type, stage and size) of cancers detected at screening affect number and nature of cancer detected symptomatically in the years after screening, numbers overdiagnosed and life years saved. We will explore how detecting greater numbers of Ductal Carcinoma in Situ (DCIS, i.e. most common form of potential precursor of invasive breast cancer) affects the benefits and harms of screening.

Using Findings to Change NHS Practice

We will use the findings to inform the UK National Screening Committee and revision of the English quality assurance guidelines for breast cancer screening. This will depend on results, but could for example include revising the targets for proportion of women recalled, of DCIS detection rates, or level of flexibility in the screening interval target.

1. Background and Rationale

What is the problem being addressed?

We do not currently know which version of breast cancer screening gives most benefit and least harm to the women who are screened. In particular, how often should women be

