1. Breast cancer mortality, as defined by the English Cancer Registry (where the initial source is the same but linkage to NBSS data more complete as uses multiple fields rather than just NHS number) checked against cause of death from the civil registrations mortality file. These sources have limited death data pre-1997, so we will also extract deaths data from NBSS to determine whether it can provide adequate quality, and if so use pre-1997. It is a binary outcome for each woman, with different lengths of follow up. Reported as cumulative incidence over all follow-up time, with focus on 10 year and 13 year to match previous systematic reviews.
2. All-cause mortality for everyone in the included cohort. This is taken from the civil registrations mortality file, which is populated by the Office of National Statistics. It is a binary outcome for each woman, with different lengths of follow up. Reported as cumulative incidence over all follow-up time, with focus on 10 year and 13 year to match breast cancer mortality.
3. Overdiagnosis. Overdiagnosis will be inferred as any difference between the study groups in total cumulative incidence of cancer (screen and symptomatic detected) after sufficient follow-up (the compensatory drop method). Therefore the outcome measured will be difference between groups in sum of breast cancers detected at screening and symptomatically. We will carefully consider length of follow-up in interpreting results relating to overdiagnosis, as insufficient follow up results in overestimation. We will publish a full protocol detailing all analysis methods and outcomes before commencing analysis to prevent selective reporting of outcomes or other analysis elements. Reported as cumulative incidence over all follow-up time, with focus on 10 year and 13 year to match breast cancer mortality.
4. Stage shift. This is defined by variables from the English Cancer Registry, including histological grade, cancer stage, and cancer size. The proposed mechanism of action of breast screening benefit is through detection of smaller earlier stage cancers. This will be measured for a combination of screen and symptomatic cancers, where differences between exposed and unexposed represents the stage shift of exposure. [In detail TNM stage (size, nodes, distant metastases), alternative nodal count to match Z11 and POSNOC trials 1/1-2/3+, DCIS vs invasive, invasive

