grade 1/2/3, DCIS grade 1/2/3, DCIS surgical size (mm), Invasive surgical size (mm), invasive cancer type, hormonal status, Nottingham Prognostic Index].

5. Morbidity. Here we are interested in the morbidity associated with breast cancer treatment. We measure this as four outcomes: women receiving breast surgery, axillary surgery, radiotherapy, and chemotherapy within one year of diagnosis. Each of these are binary outcomes for each episode of cancer for each woman.
6. False positive recalls. These are women recalled from screening for extra tests but those extra tests do not indicate cancer. These data are taken from the NBSS computer system which automatically records who is recalled. This is measured as any women who were recalled but did not have cancer detected in follow up tests. It is a binary outcome for each episode of screening for each woman. This is an important harm of screening because it is associated with increased anxiety in women screened.

We will investigate the mechanism of action linking the three exposures to the outcomes. In particular we will investigate the relationship between characteristics of cancer detected, and women's outcomes such as overdiagnosis and mortality and morbidity associated with treatment. This analysis has dual purposes: firstly when inferring causation from observational research, in addition to appropriate accounting for confounding, it is important to elucidate the mechanism of action. Secondly, it is an important research output in its own right, to provide the evidence base for policy-makers to link the characteristics of cancers detected to benefits and harms of screening, when assessing a range of changes to screening. In the UK and Australia this is referred to as the linked evidence approach, and the US Preventative Services Task Force refer to it as the dotted line in the analytic framework.

How do two extra invitations to screening between the ages of 65 and <71 years affect all-cause and breast cancer specific mortality, overdiagnosis, treatment associated morbidity, and false positive recalls, in women already invited to screening age 50-64? (analysis led by [name], carried out at Bristol)

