The NHS Cancer plan(4) extended the age range of breast screening in England from 50-64 years to 50-70 years, which was rolled out across all 80 centres between the years 2000 and 2006. The first sites to adopt the age extension were those piloting the introduction of the assistant practitioner role to assist radiographers in their work, as part of the introduction of the four tier workforce.(24) After these pilot sites, timing of roll out to other sites was dependent on funding, staffing and extra mammography equipment in place. The provision of extra equipment was lottery funded.

Within the 2000-2006 time period we will compare outcomes in women who were and were not offered two extra rounds of screening, adjusting for temporal, centre and individual level confounding. We will use the approach described by García-Albéniz et al.,(20) to emulate a weekly series of trials in which eligible women who have not yet been offered additional screening are assigned to receive or not receive screening in the coming month. Women will become eligible for the first trial on their 64th birthday*, and each woman will contribute to subsequent trials providing that she remains eligible until the day before she turns 71. We will make two sets of comparison: (a) no additional screening compared with one or more invitations to additional screening; and (b) at least two additional invitations compared with no or one additional invitation. For each weekly trial, follow-up in women in the "less screening" group will be censored at the time that receive sufficiently many invitations for inclusion in the "more screening" group. We will use inverse probability weights to adjust for

selection bias introduced by such censoring. Standard errors will be adjusted for inclusion of women in multiple weekly trials. Analyses will be by intention to screen, with women included in each group regardless of whether they attended screening. We will limit the analysis to years in which some centres had and others had not rolled out the screening age extension. We will model changes in the rate of each outcome with calendar time using cubic splines. Self-referral to screening in the years after screening will attenuate any effect, but fewer than 12% of women self-refer. **Preliminary investigation will be necessary to ascertain how the upper age limit of 64 was implemented, as it may in practice have been until a womans 65th birthday*

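### Treatment morbidity and false positive recalls are fixed per cancer and per screening episode, denominators that the age and interval exposures themselves change

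*Protocol*

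**What the plan says.** Under Measuring Outcomes, the list headed as primary outcomes gives six items. Two of them carry two units each.

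- Item 5, morbidity, begins with women: "We measure this as four outcomes: women receiving breast surgery, axillary surgery, radiotherapy, and chemotherapy within one year of diagnosis". It then fixes the unit: "Each of these are binary outcomes for each episode of cancer for each woman".
- Item 6, false positive recalls, also begins with women: "This is measured as any women who were recalled but did not have cancer detected in follow up tests". It then says: "It is a binary outcome for each episode of screening for each woman".

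The two mortality outcomes in the same list are defined differently: "It is a binary outcome for each woman, with different lengths of follow up". Mortality and overdiagnosis are both reported as cumulative incidence, with a focus on 10 and 13 years. Items 5 and 6 have no such summary.

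Both items are named in the age-extension, interval and recall-threshold questions of Work Package 2. For the age question the protocol adds: "Analyses will be by intention to screen, with women included in each group regardless of whether they attended screening". The Research Plan, in the summary, speaks of counts: "These benefits and harms will include numbers of false positive recalls, overdiagnosed cases, and mortality".

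**The concern.** The age and interval questions are set up as target trials. Women are classified at time zero, and the exposure is how many invitations they get or how closely spaced those are. The number of screening episodes is then a direct product of the exposure, and the number of cancers diagnosed can be one too. A proportion per episode or per cancer divides by a quantity that the exposure has altered. It no longer compares the groups as formed, and it leaves out women with no episode or no cancer, whom the intention-to-screen rule keeps in.

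These two outcomes carry the treatment burden and the false alarms of more screening. They are also two of the three outcomes in the heading of the interval question. If each extra screen behaves like the others, a per-episode analysis reports no difference in false positives however many more screens one group receives.

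**Working it through.** **Is the episode unit only a way of recording data?** Table 1 (Sample Size Requirements) gives false positives as 3.1%, change 0.1%, 641,114 per group, at 90% power and 5% significance. The two-sided, pooled-variance formula for two proportions at 3.1% vs 3.2% gives:

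n = [1.960·√(2·0.0315·0.9685) + 1.282·√(0.031·0.969 + 0.032·0.968)]² / 0.001² = 641,114, an exact match.

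The 3.1% is evidently a per-screen rate. Recall is 3.9% per appointment (Background and Rationale) and screen-detected cancer 8.4/1000 (Table 1), so 3.9% − 0.84% = 3.06%. The protocol's own calculation for this outcome therefore treats the episode as the unit of comparison.

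**False positives, interval question.** Inputs: 3.1% per episode in both groups; bands of 15–27 and 28–40 months, midpoints 21 and 34. Assumptions: sustained intervals and full attendance for the rates (equal attendance is enough for the ratio).

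- Per episode: 3.1% − 3.1% = 0.
- Per 1,000 woman-years: 31 × 12/21 = 17.7 and 31 × 12/34 = 10.9.
- Ratio: 34/21 = 1.62. Closest band edges: 28/27 = 1.04. Furthest: 40/15 = 2.67.
- Women ever affected over 6 years, taking 24- and 36-month rounds and independent episodes: 1 − 0.969³ = 9.0% vs 1 − 0.969² = 6.1%. The per-episode rate with shorter rounds would have to fall to about 2.1% before these were equal.
- If each group contributes one round only, there is one episode per woman in both, and the two units agree.

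**False positives, age question.** In comparison (a) the less-screened group has no additional invited episode. A per-episode rate there could come only from women screened without an invitation, and the protocol says "fewer than 12% of women self-refer". Per woman, two extra screens against none is 6.1% vs 0% from invited screens, on the same assumptions.

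**Morbidity.** Let C be cancers per 1,000 women with less screening, E the extra cancers with more, p the treated share of the C cancers (unchanged), and q the treated share of the extra ones.

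- Per-cancer share with more screening: (Cp + Eq)/(C + E), which is below p whenever q < p.
- Treated women: Cp + Eq, which exceeds Cp whenever q > 0.

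So for 0 < q < p the per-cancer share falls while treated women rise. If q = p, the share does not move and treated women rise by E/C.

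For scale, the protocol's counts give 250,000/10 million = 25.0 screen-detected cancers per 1,000 women. Interval cancers add 35 million × 2.9/1000 / 10 million = 10.2, so C is about 35.2, excluding cancers after screening ends. Take E = 1 per 1,000, which is the change in the overdiagnosis row of Table 1 and not a forecast.

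- q = p: treated women rise by 1/35.2 = 2.8%. With an assumed C of 65 the rise is 1/65 = 1.5%.
- q = p/2 (assumed), C = 35.2: the share becomes (35.2 + 0.5)/36.2 = 0.986 of p, a fall of 1.4%, while treated women rise by 0.5/35.2 = 1.4%.

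**The case against.** The strongest reply is that the phrases describe how events are recorded. Both end with a reference to each woman, the same formula is used for interval and screen-detected cancers, and records per episode can be summed per woman. The design sections point the same way: survival methods, emulated trials of eligible women, cloned follow-up of each woman, and the intention-to-screen rule. That a per-episode rate is nearly undefined in age comparison (a) is itself a reason to doubt that it was intended. A statistical analysis plan, or the full protocol promised before analysis, may settle the matter.

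Much of this stands. A reader might infer that the study will certainly compare shares of episodes and cancers; the documents do not say so. But they never say the opposite for these two outcomes, the definitions contradict themselves within an item, and Table 1 uses the per-screen rate.

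Three further inferences should be resisted.

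- *That extra cancers would go unseen.* Overdiagnosis is listed in the age and threshold questions, and Objective 2 lists it for all three exposures, although the heading of the interval question omits it. It would show extra cancers, but not how many women received each treatment.
- *That recall results for self-referred women are missing.* Appendix 2 mentions only appointment dates for non-routine episodes, but it is a summary. Work Package 1 says the full variable definitions are in a separate document.
- *That the per-episode result will point the wrong way.* For false positives this needs a lower per-episode rate with shorter intervals, which the documents do not give.

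The per-episode unit is also right for the single-round threshold model (model 2), where each episode is the exposed unit. Morbidity is not among that model's outcomes.

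**Conclusion.** The point holds for the age and interval questions and, for morbidity, for the longer-horizon threshold models (1 and 3), where the threshold can change the number of cancers. Followed as written, the two definitions give contrasts on post-exposure denominators, at odds with the intention-to-screen analysis of the age question. Those contrasts can miss a rise in women treated or falsely recalled.

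The false positive ratio of 1.62 (1.04 to 2.67) depends on an equal 3.1% per-episode rate, sustained intervals and equal attendance, and disappears in a one-round contrast. The direction of the morbidity result is algebra, given unchanged treatment of the other cancers. Its size is assumed, and is a few per cent or less in the illustrations above. This is a definition that should be corrected before analysis. It does not show that any result will be wrong.

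**What to change.** In items 5 and 6 of the primary outcomes, for the age and interval questions, state the main measure per eligible woman from time zero over a common horizon:

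- morbidity: cumulative incidence of each of the four treatments, with women without cancer counted as untreated;
- false positives: the proportion of women with at least one false positive recall, and the mean number per woman.

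Use the same per-woman morbidity measure in threshold models 1 and 3. Keep per-cancer and per-episode proportions as descriptive outputs, and keep per-episode false positives as the measure for threshold model 2.

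The cost is a rewording of two definitions and the matching analysis code. The tables already link by a pseudonymised identifier (Appendix 2), so the change of unit needs no new linkage.

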Appendix 1 – Letter of Support [redacted]

Appendix 2: Data requested and reason

Table 1: National Breast Screening Research Dataset (NBSRD) Patient Demographics data to be provided to the applicant in accordance with the cohort inclusion and exclusion criteria.

To include one row per woman included, with pseudonymised identifiers to link between tables, with ethnicity, month and year and cause of death, month and year of birth, participation in relevant research trials, and issues with data quality of NHS number.

Table 2: National Breast Screening Research Dataset (NBSRD) breast screening episode data for routine population screening episodes to be provided to the applicant in accordance with the cohort inclusion and exclusion criteria

To include one row per screening episode, with pseudonymised identifiers to link between tables, screening date, pseudonymised identifiers for the radiologists examining the mammograms, their decisions, whether the woman was recalled for further tests, whether cancer was detected.

Table 3: National Breast Screening Research Dataset (NBSRD) mammographic features to be provided to the applicant in accordance with the cohort inclusion and exclusion criteria.

Details of mammographic features associated with detected cancers. Data will be provided for screen detected breast tumours only. Features to include side of the body, mammographic characteristics such as mass or calcifications.

Table 4: National Breast Screening Research Dataset (NBSRD) cancer tumour data to be provided to the applicant in accordance with the cohort inclusion and exclusion criteria.

Tumours will be limited to C50 (breast cancer) or D05 (Breast DCIS or LCIS) records, or the pre-1995 equivalents in of '174' and '2330' respectively, only, inclusive of both screen detected and symptomatically detected breast tumours. Includes ICD classification, morphology, behaviour, grade, size, number of involved nodes, oestrogen, progesterone and HER2 status, Nottingham Prognostic Index, TNM stage, and whether screen detected.

Table 5: National Breast Screening Research Dataset (NBSRD) cancer treatment data to be provided to the applicant in accordance with the cohort inclusion and exclusion criteria.

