Treatment detailed will be restricted to records for the treatment of C50 or D05, or the pre-1995 equivalents in of '174' and '2330' respectively, (inclusive of screen detected and symptomatically detected breast tumours). Includes all events those occurring within the first 365 days from DATEOFDIAGNOSISBEST. All other event dates will be excluded. Treatment includes chemotherapy, radiotherapy and surgery.

Table 6: National Breast Screening Research Dataset (NBSRD) derived ‘First Event’ data to be provided to the applicant in accordance with the cohort inclusion and exclusion criteria.

Events will be restricted to first procedure NCRAS is aware of for a C50 or D05, or the pre-1995 equivalents in of ‘174’ and ‘2330’ respectively, within the first 365 days from DATEOFDIAGNOSISBEST. All other event dates will be excluded. Datasources include registration data supplemented with SURGERYETC and OTHERPROCEDURES; HES; SACT; RTDS.

All dates and events for this table to be taken from multiple sources as described in the ‘Custom fields’ tab of the data dictionary. Includes breast surgery (breast conserving, mastectomy) underarm surgery (axillary clearance, sentinel lymph node biopsy), hormone therapy, radiotherapy, chemotherapy.

Table 7: National Breast Screening Research Dataset (NBSRD) breast screening episode data for non-routine screening episodes (high risk, GP/self-referral, non-routine recall) to be provided to the applicant in accordance with the cohort inclusion and exclusion criteria

To include date of any appointments for mammography which were not defined as screening appointments, such as GP referral.

Table 8: IMD Score – to be based upon last known address in both NCRAS and NBSS.

Index of multiple deprivation for woman’s last known address only.

Table 9: Cause of date from the civil registration mortality file.

Month and year of death and cause for main study outcome. Cause primarily to separate breast cancer death from other causes, with sensitivity analyses defining this using combinations of underlying and secondary cause. ICD10 code C50 in underlying cause is main indicator for breast cancer death. However ICD10 code C76 multiple cancers may include some breast cancer details, to check this will use ICD10 secondary cause, and refer death certificate data death cause code 1a,b,c and 2 to clarify.

Table 10 Cause of death from cancer registry

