- *Table 6: Cancer Registry Derived 'First Event' data restricted to first procedure of each type the Cancer Registry is aware of for a C50x or D05x or the pre-1995 equivalents in of '174' and '2330' respectively, within the first 365 days from DATEOFDIAGNOSISBEST in Table 4. All other event data will be excluded. Data sources include registration data supplemented with SURGERYETC and OTHERPROCEDURES; HES; SACT; RTDS. All dates and events for this table to be taken from multiple sources as described in the 'Custom fields' tab of the data dictionary.*
- *Table 7: NHS National Breast Screening Programme (non-routine episode) data from BS Select will be restricted to women in Table 1. Records with no invitation to screening will be excluded from Table 7. Records in Table 7 will be restricted to records with date of first offered appointment either (i) null or (ii) from screening programme inception in 1988 to 31/03/2018*
- *Table 8: IMD Score data will be based upon last known address in NBSS.*
- *Table 9: MBIS civil registration mortality data be provided for all women identified in Table 1 and recorded in MBIS as deceased, updated in 2021.*
- *Table 10: NCRAS death data to be provided for all women identified in Table 4 and recorded in NCRAS as deceased*

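### As the data request is described, false positive recalls at self-referred screens would go uncounted, so self-referral would not dilute this harm of the age extension as it dilutes mortality and overdiagnosis

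*Protocol*

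**What the plan says.** Protocol, Measuring Outcomes, primary outcome 6 defines a false positive as a woman recalled in whom the further tests find no cancer. The source is stated as "These data are taken from the NBSS computer system which automatically records who is recalled", and the unit as "It is a binary outcome for each episode of screening for each woman. This is an important harm of screening". The text does not say whether a self-referred screen counts as an episode of screening.

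Appendix 2 describes two episode tables:

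- **Table 2** is "breast screening episode data for routine population screening episodes to be provided to the applicant". Its listed content includes "whether the woman was recalled for further tests, whether cancer was detected".
- **Table 7** is "breast screening episode data for non-routine screening episodes (high risk, GP/self-referral, non-routine recall"). Its description in full is "To include date of any appointments for mammography which were not defined as screening appointments, such as GP referral".

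Appendix 3 gives the Table 7 source as "non-routine episode) data from BS Select will be restricted to women in Table 1", and removes from it any record without an invitation.

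The age-extension section of Work Package 2 analyses women by intention to screen. Comparison (a) sets no additional screening against one or more additional invitations. Comparison (b) sets at least two additional invitations against none or one. On self-referral it says: "Self-referral to screening in the years after screening will attenuate any effect, but fewer than 12% of women self-refer".

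**The concern.** Outcome 6 needs two facts per episode: that the woman was recalled, and that no cancer was found. On the Appendix 2 descriptions, both are available for routine episodes and neither for self-referred ones.

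In comparison (a), a woman in the uninvited group has no routine invitation beyond the age limit and is censored if one arrives. Her route to NHS screening is therefore mainly self-referral. If recalls at those screens are not in the data, this group's false positive count is close to zero because of how the data were requested, not because it was observed to be so.

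Deaths and cancers are different. They come from the mortality file and the cancer registry whatever route led to the screen, so self-referral does dilute the contrasts for mortality and overdiagnosis. The protocol's remark about dilution covers every effect. It would not hold for false positives counted from Table 2 alone. A study meant to weigh benefit against harm would then have one harm undiluted and the other outcomes diluted.

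**Working it through.** **1. Can another table fill the gap?** Appendix 3 limits Table 3 to episodes in Table 2, and Appendix 2 limits it to screen-detected tumours. Table 4 holds tumours, not recalls. No other table is described as carrying recall at a self-referred screen. Dropping Table 7 records without an invitation could also remove self-referrals altogether, depending on how the invitation field is coded for them.

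**2. The plan's own figure.** Table 1 under Sample Size Requirements gives 641,114 per group for false positive recalls, at baseline 3.1%, change 0.1 point, 90% power and 5% significance. The two-sided comparison of 3.1% with 3.2%, with pooled variance and no continuity correction, returns 641,114 exactly. The figure is not in dispute; it supplies the rate f = 3.1% per screen.

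**3. Inputs for the bound.**

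- f = 3.1% (Table 1 baseline, not specific to ages 65 to 70; assumed to apply at self-referred screens too).
- s = 12%, the protocol's upper limit on self-referral, placed wholly in the uninvited group as the worst case. The protocol gives no split by group.
- v = visits per self-referrer over the period. Not given; assumed 1 or 2.
- u = uptake of each extra invitation. Not given; assumed 60% to 100%.
- Two extra rounds, as the question is posed.

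**4. Formulas**, as expected false positives per 100 women:

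- Counted in the invited group: 2 × u × f
- Missed in the uninvited group: s × v × f
- Relative overstatement: missed ÷ (counted − missed)

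**5. Results at s = 12%.** Counted in the invited group: 2 × 0.60 × 3.1 = 3.72, up to 2 × 1.00 × 3.1 = 6.20.

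| Visits | Missed | Overstatement, u = 60% | Overstatement, u = 100% |
|---|---|---|---|
| 1 | 0.12 × 3.1 = 0.372 | 0.372 ÷ 3.348 = 11.1% | 0.372 ÷ 5.828 = 6.4% |
| 2 | 0.744 | 0.744 ÷ 2.976 = 25.0% | 0.744 ÷ 5.456 = 13.6% |

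**6. Lower self-referral.** At s = 3% with one visit, 0.093 is missed and the overstatement is 0.093 ÷ 3.627 = 2.6% down to 0.093 ÷ 6.107 = 1.5%.

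**7. Self-referral in the invited group.** These recalls would also be missed, so only the difference between groups matters. With 12% in the uninvited group and one visit, the net missed difference is (12% − x) × 3.1, where x is the invited group's share: 0.37 at x = 0, 0.28 at 3%, 0.19 at 6%, and 0 at 12%.

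**8. Comparison (b).** The less-screened group includes women with one additional invitation. Their routine recalls are in Table 2, so the group's count is not near zero and only its self-referred part is lost.

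**The case against.** The strongest reply is that Appendix 2 is a summary. The version history says the data tables were moved to a separate file and the appendix was broadened, and Work Package 1 says all variables are fully defined in a separate document. The summary is visibly incomplete. Table 7 is filtered on invitation, so it must hold more than a date. The Table 2 description leaves out attendance, which Work Package 1 lists as held. Table 7 is also headed as episode data, like Table 2. It may therefore carry recall and result after all. This stands, and it makes the consequence conditional. It does not dispose of the point: the same summary names recall and result for one table and only dates for the other, the source of Table 7 is not the stated source of outcome 6, and the outcome definition is silent on self-referred screens.

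A reader might infer more: that the outcome is restricted to routine episodes, that this harm is certainly overstated, and that the balance for extending to age 70 is tilted towards harm. The documents do not support this. Outcome 6 contains no such restriction, the variable file is not shown, and the split of self-referral by group is not given.

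A reader might also set the missed 0.37 points against the 0.1 point change in Table 1 and call it 3.7 times too large. That 0.1 is a generic detectable change. The relevant yardstick is the age-extension contrast itself, some 3.3 to 5.8 points in the one-visit case above. Reading the 12% ceiling as 12% screened in every round also goes beyond the text, which limits the share of women, not visits.

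Details of which tables feed an outcome often belong in an analysis plan. Here, however, the protocol makes a general statement about dilution that its own described data would not bear out for one primary outcome.

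**Conclusion.** The point holds conditionally. If the separate file does not supply recall and result for self-referred and GP-referred episodes, false positives at those screens go uncounted, mainly in the uninvited group of comparison (a) and less so in comparison (b). The contrast would then not be diluted by self-referral in the way mortality and overdiagnosis are, and would be overstated if uninvited women self-refer more than invited women.

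The 6% to 25% range is a worst case: it takes the protocol's ceiling, no self-referral among invited women, and the assumed uptake and visits. The true figure could be far lower, down to zero. Nothing in the range reverses the direction of the effect. This concerns the completeness and labelling of one outcome, not whether extra invitations produce false positives.

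**What to change.** 1. Define outcome 6 as false positive recall at any NHS breast screening episode, whether routine, self-referred or GP-referred, counted the same way in both groups.
2. Confirm that recall and assessment-result fields are supplied for Table 7 episodes. If not, add them, from the NBSS extracts already taken from the centres if those hold them.
3. Do not drop self-referred episodes from Table 7 for want of an invitation.
4. If the fields cannot be supplied, label the result *false positive recalls at routinely invited screens* and do not claim dilution by self-referral for it. Report a bound by group: Table 7 self- and GP-referral appointments multiplied by the age-specific false positive rate from Table 2.

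The cost is a sentence in the outcome definition and a few fields in a request that already covers these episodes, or one added calculation. If self-referral is higher among uninvited women, the stated harm becomes slightly smaller.
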